- Is of child-bearing potential, and is either pregnant or interested in becoming pregnant during the duration of the study;
- Medically significant obesity as defined by a Body Mass Index (BMI) of > 40 kg/m². BMI = (weight in pounds \times 703) \div (height in inches \times height in inches);
- Active malignancy: a history of any invasive malignancy (except non-melanoma skin cancer), unless the patient has been treated with curative intent and there have been no clinical signs or symptoms of the malignancy for at least 5 years;

- Known allergy to cobalt chromium or titanium;
- Used any investigational drug or device within the past 30 days;
- Pending litigation related to back pain or injury;
- Is a prisoner.

Primary Endpoint: The primary study endpoint for this study is individual patient success at 24 months. Individual patient success will be defined as follows:

- Improvement in the ZCQ by a minimum of 0.5 for both Symptom Severity (SS) and Physical Function (PF) scores at 24 months as compared to baseline.
- Maintenance or improvement in neurological outcome at 24 months.
- No subsequent surgical intervention at the level of treatment (including device failures requiring revision, removal, re-operation and supplemental fixation).
- No serious device-related adverse events.

Secondary Endpoints:

- Maintenance or improvement of the components of the primary ZCQ;
- Maintenance or improvement in patient function, as measured by the Oswestry Disability Index (ODI) questionnaire;
- Maintenance or improvement of the leg and back VAS pain scores;
- Maintenance or improvement in the components of the SF-36 Quality of Life Questionnaire;
- Changes in quantitative radiographic measures including disc height, vertebral range of motion and translation;
- Changes in qualitative radiographic measures including fusion; assessment, device migration and presence of radiolucencies;
- Radiographic Success
- Maintenance or improvement in neurological status;
- Incidence, severity and device or procedure relatedness of all adverse events over the 24-month study assessment period;
- Components of primary endpoint (surgical revisions, reoperations, removals, supplemental fixation);
- Return to normal activities of daily life;
- Change in work status and time to return to work;
- Narcotic medication usage;
- Length of hospital stay;
- Duration of surgical procedure and instrumentation time;
- Blood loss;
- Rehabilitation utilization.

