1.3 Purpose

The purpose of this study is to evaluate the safety and effectiveness of the AFRS in patients with lateral, lateral recess and/or central canal stenosis due to facet degeneration at a single level from L3 to S1 who require a lumbar decompression and facetectomy compared to an instrumented posterolateral fusion control group. Safety of the AFRS device will be evaluated by the incidence, severity and device or procedure relatedness of all adverse events over the 24 month assessment period as compared to the control group. Effectiveness of the AFRS will be based on the improvement in symptom-related questionnaire scores, function, and neurological status.

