1.5 Study Objectives

The primary objective of this study is to evaluate the safety and effectiveness of the AFRS device through 24 postoperative months compared to an instrumented posterolateral fusion procedure.

More specifically, the primary study objective is to demonstrate that patient success, evaluated at 24 months in patients treated with the investigational device, is not inferior to subject success at 24 months in patients treated with the control procedure, where patient success is based on the following defined measures: The Zurich Claudication Questionnaire (ZCQ), neurological deficit, and the need for subsequent surgical intervention (at the level of treatment) and/or device removal and absence of serious, device-related adverse events.

Patients will also be evaluated during the course of the study for all adverse events and surgical interventions, and the relationship of these events and interventions to the investigational device. All adverse events and surgical interventions will be tabulated and reported for each assessment time period.

[Redacted]

[Redacted]

[Redacted]

[Redacted]

[Redacted]

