8.0 STATISTICAL ANALYSIS PLAN

8.1 Analysis Populations

Primary Analysis Population:

The principal analysis of the primary and secondary endpoints will utilize the intent-to-treat (ITT) patient population. The ITT population will include all randomized subjects for whom surgery is attempted. Subjects for whom surgery is attempted but not successfully completed will be considered treatment failures. Randomized subjects in whom surgery is not attempted will be described in detail in a separate section of the study report.

Secondary Analysis Populations:

The primary and secondary objectives will be further analyzed using an as-treated (AT) analysis performed on all randomized subjects according to the treatment actually received.

The primary and secondary objectives will be further analyzed using a per protocol (PP) analysis performed on an evaluable patient population. The evaluable population will consist of all ITT subjects that: [1] meet critical study eligibility criteria and have no significant protocol deviations based on Clinical Events Committee assessment; [2] have the assigned procedure completed; and [3] completed the 24-month follow-up assessment.

Training Population:

This patient population will include all non-randomized AFRS treated patients enrolled during the pivotal phase of the trial as training cases at the site. A maximum of two patients per site for a total of 60 patients will be included in this cohort. Training cases will be described separately from randomized patients in the final study report and will be presented primarily using descriptive statistics. This patient population will be used to understand the learning curve in the use of the device by assessing the results of the Training cases relative to those obtained in the Treatment group arm of the randomized study.

An additional presentation of the safety data in which all of the patients treated with the AFRS device (non-randomized and randomized) are combined as one cohort and compared to the control group will be included.

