8.3 Randomization, Sample Size, and Analysis Plan

This study is designed to adaptively determine the proper sample size. Possible sample sizes are 300, 450, 600, and 750 (maximum). Randomization will follow a 2:1 (treatment:control) allocation ratio and be stratified by site, using a blocked randomization scheme with blocks of randomly varying sizes. Further details on the randomization process are provided in **Section 5.2**.

In addition to the planned interim analyses that will determine the sample size, there will be several interim analyses conducted for the purpose of possibly declaring an early win. The first of these will occur when 300 subjects have completed 2 years of follow-up. If the trial does not stop for success at that analysis, a second analysis will occur when 450 have completed 2 years of follow-up. If the trial does not stop for success at that analysis, a final analysis will occur when the entire enrolled cohort has completed 2 years. It is not necessary for the trial to have stopped enrollment in order for the interim “Early Win” analyses to occur. For example, the first Early Win analysis (when 300 have completed 2 years) will occur even if the trial is still enrolling (i.e., the sample size determination algorithm has not determined the final sample size). Of course, if the final sample size is 300, there can be only 1 Win analysis (when the full cohort has reached 2 years); if the final sample size is 450, there can be only 2 Win analyses (when 300 have reached 2 years and when the full cohort has reached 2 years).

The sample size determination analyses and the “Early Win” interim analyses are triggered by different circumstances (number enrolled versus number completing 2 years) and are expected to follow different analysis schedules (i.e., although it is possible, a sample size analysis and an early win analysis are unlikely to occur simultaneously).

Further details on this analysis plan are given below.

Determination of Non-Inferiority and Superiority (“Win” Analyses)

Interim “Win” analyses are scheduled to occur when 300 and 450 subjects have completed 2 years of follow-up. A final analysis will occur when the entire enrolled cohort has completed 2 years of follow-up. At each of these analyses, the probability of non-inferiority $\Pr(H_{\delta=0.15} | \text{data})$ will be calculated, based on all observed data, including predicted 2-year outcomes for those subjects who have not reached 2 years.

[REDACTED]

[REDACTED]

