The leg pain VAS scores for subjects in each treatment group will be summarized separately by the more symptomatic and less symptomatic legs of each subject, as measured at baseline. For inference, the relevant hypothesis is

$$H: \mu_t - \mu_c < 0$$

where μ_t and μ_c are the average VAS scores for the more symptomatic legs (or less symptomatic legs, as appropriate) in the treatment and control groups, respectively.

Oswestry Disability Index (ODI)

The ODI scores for subjects in each treatment group will be summarized at the 3-, 6-, 12-, and 24-month time points. For the 24-month time point, a statistical test will be conducted. The relevant hypothesis is

$$H: \mu_t - \mu_c < \delta$$

where μ_t and μ_c are the average ODI scores in the treatment and control groups, respectively.

[REDACTED]

[REDACTED]

Adverse Events

All Adverse Events (AEs) will be tabulated and summarized as counts and percentages by treatment group. AEs will also be cross-tabulated separately according to treatment group and:

- Severity (Mild, Moderate, Severe)
- Seriousness (Serious, Non-serious)
- Device-Relatedness (Related, Not Related)
- Surgery-Relatedness (Related, Not Related)

In addition, the occurrence of any Unanticipated Adverse Device Effects (UADE) will be listed. The classification of severity, relatedness, and anticipated nature of AEs will be made by the Clinical Events Committee (CEC).

Summaries will include counts, percentages, and 95% Bayesian credible intervals for the difference in proportions between treatment groups. An analysis of safety outcomes which combines all AFRS treated patients (randomized and non-randomized) compared to control patients will also be performed. The statistical method for dichotomous outcomes (e.g., device-relatedness, surgery-relatedness) will be the Bayesian version of a comparison of proportions, described below. The statistical method for trichotomous outcomes (e.g., Severity) will be the Bayesian version of a comparison of polytomous outcomes, described below.

Surgical Revisions, Reoperations, Removals, and Supplemental Fixation

The incidence of a composite of surgical revisions, reoperations, removals, and supplemental fixation at the index level for subjects in each treatment group will be summarized at the 3-, 6-, 12-, and 24-month time points. For the 24-month time point, a statistical test will be conducted. The relevant hypothesis is

$$H: p_t - p_c < 0$$

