where p_t and p_c are the proportions of subjects in the treatment and control groups, respectively, who experience one or more of the defining surgical events. The statistical method will be the Bayesian version of a comparison of proportions (with predictions), described below.

Radiographic Measurements

[figure not shown]
Radiographic measurements in each treatment group will be summarized at the 3-, 6-, 12-, and 24-month time points. Continuous radiographic endpoints are disc height, vertebral range of motion, and translation. For these, statistical summaries will include means, medians, standards of deviation, and 95% central Bayesian credible intervals for the means and mean differences over time between treatment groups, where appropriate. Dichotomous radiographic endpoints are fusion, device migration, and the presence of radiolucencies around the hardware and screws. For these, statistical summaries will include proportions and 95% Bayesian credible intervals for the proportions and, where appropriate, the difference in proportions between treatment groups.

Return to Normal Activities of Daily Life

The proportion of subjects able to return to “Most” or “All” of the activities of daily life will be summarized at the 3-, 6-, 12-, and 24-month time points. Statistical summaries will include proportions and 95% Bayesian credible intervals for the proportions and the difference in proportions between treatment groups. The statistical method will be the Bayesian version of a comparison of proportions, described below.

Return to Work

For subjects in each treatment group, the time from date of surgery to date of return to work will be computed and summarized with descriptive statistics. It is possible that some subjects will never return to work and be censored in this analysis, either at the end of the study or at the point of death or loss to follow-up, so the statistical technique will be the Bayesian Survival Analysis, described below.

[REDACTED]

[REDACTED]

[REDACTED]

[REDACTED]

ZCQ Patient Satisfaction Domain Score

The ZCQ Patient Satisfaction domain scores will be summarized for subjects in each treatment group at the 3-, 6-, 12-, and 24-month time points. For the 24-month time point, a statistical test will be conducted. The relevant hypothesis is

$$H: \mu_t - \mu_c > 0$$

where μ_t and μ_c are the average satisfaction scores in the treatment and control groups, respectively. [REDACTED]

[REDACTED]

[REDACTED]

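### Adverse events are compared as crude percentages, so 24-month incidence is understated in both arms if the tables are cut at an early win

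*Combined protocol and SAP*

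**What the plan says.** **Horizon.** Section 1.3 judges safety by the incidence, severity and "relatedness of all adverse events over the 24 month assessment period as compared to the control group". The secondary endpoint list in the Protocol Summary likewise covers "all adverse events over the 24-month study assessment period".

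**Method.** Section 8.7 states: "All Adverse Events (AEs) will be tabulated and summarized as counts and percentages by treatment group". It adds: "Summaries will include counts, percentages, and 95% Bayesian credible intervals for the difference in proportions between treatment groups". For dichotomous outcomes it names a Bayesian comparison of proportions. It mentions no time at risk, censoring or prediction for AEs.

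**Timing.** Section 8.3 schedules win analyses at 300 and 450 two-year completers and states "It is not necessary for the trial to have stopped enrollment in order for the interim" win analyses to take place. Possible final sizes are 300, 450, 600 and 750.

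**Other endpoints.** In the same section, the composite of revisions, reoperations, removals and supplemental fixation uses the "Bayesian version of a comparison of proportions (with predictions), described below", and return to work uses a survival analysis because of censoring. Section 8.6 predicts missing two-year outcomes for the primary endpoint.

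**By-period reporting.** Section 1.5 promises: "All adverse events and surgical interventions will be tabulated and reported for each assessment time period". No denominators are given.

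**Pooled cohort.** Section 8.1 adds a safety presentation in which all AFRS patients are merged: "non-randomized and randomized) are combined as one cohort and compared to the control group".

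**The concern.** A crude percentage counts a patient operated on last month in the same denominator as one with two full years. Section 8.1 uses all randomized patients with attempted surgery for the secondary endpoints, so as written recent patients are in the AE denominator. The result does not estimate the 24-month incidence that section 1.3 asks about; it falls below it whenever events continue after surgery and follow-up is incomplete.

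The loss is greatest for late events. Section 6.1.1 lists component degradation, reaction to wear debris, bone resorption and adjacent-level degeneration as possible AEs. Any of these that arise in the second year are missed most, in a trial whose device is meant to preserve motion over time. The plan allows for incomplete follow-up in neighbouring endpoints, but the AE paragraph does not.

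**Working it through.** The documents give no AE rates and no expected follow-up at a win look, so there is no planned figure to reproduce. Accrual pattern, AE rates and event timing below are assumptions.

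**Inputs.** Looks at k = 300 and 450 completers and final sizes N up to 750 (section 8.3); enrollment over T = 48–60 months (section 3.3); 15% loss to follow-up (section 3.1); up to 60 training cases (section 8.1). Assumed: even accrual and an illustrative 24-month rate of 20%. Loss to follow-up is ignored until step 5.

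**1. Share with 24 months at the look.** Look time t = kT/N + 24; enrolled = min(N, Nt/T); share s = k/enrolled.

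| k | N | T (months) | t (months) | Enrolled | s |
|---|---|---|---|---|---|
| 300 | 750 | 48 | 43.2 | 675 | 44% |
| 300 | 750 | 60 | 48.0 | 600 | 50% |
| 300 | 600 | 48 | 48.0 | 600 | 50% |
| 300 | 600 | 60 | 54.0 | 540 | 56% |
| 300 | 450 | 48 | 56.0 | 450 | 67% |
| 450 | 750 | 48 or 60 | 52.8 or 60.0 | 750 | 60% |
| 450 | 600 | 48 or 60 | 60.0 or 69.0 | 600 | 75% |

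When the look is at the full cohort, s is 100%.

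**2. What a true 20% reads.** In the first four rows, follow-up among non-completers is uniform on 0–24 months, so crude = s × 20% + (1 − s) × m, where m is their mean event probability.

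- Constant hazard: λ = −ln(0.8) = 0.2231 and m = 1 − 0.2/0.2231 = 10.4%. With s = 0.444, crude = 8.9 + 5.8 = 14.7%; with s = 0.556, crude = 11.1 + 4.6 = 15.7%.
- Events spread evenly over months 12–24 only: m = 20% × 1/4 = 5%. Crude = 8.9 + 2.8 = 11.7% and 11.1 + 2.2 = 13.3%.
- N = 450, T = 48: non-completers have 8–24 months, m = 13.7% under a constant hazard, and crude = 13.3 + 4.6 = 17.9%.

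The 48–58 month study duration in the Protocol Summary implies faster enrollment, about 18–30 months (48 − 24 − 6 to 58 − 24 − 4). With N = 750 over 20 months, s at the look at 300 falls to 40%, but every patient has at least 12 months and a constant-hazard 20% reads 17.2%.

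**3. Arm differences.** Look at 300, N = 600 or 750, T = 48–60, same follow-up in both randomized arms. In the last two rows each arm has a probability a at surgery and then a constant-hazard probability b by 24 months: event probability at follow-up f is 1 − (1 − a)(1 − b)^(f/24).

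| Pattern | True 24-month difference | Crude difference |
|---|---|---|
| Constant hazard, 20% v 15% | 5.0 points | 3.7–4.0 |
| Months 12–24 only, 20% v 15% | 5.0 points | 2.9–3.3 |
| Difference at surgery only: a = 20% v 10%, b = 10% in both (28.0% v 19.0%) | 9.0 points | 9.2–9.3 |
| Early AFRS excess, control catches up: a = 20% v 10%, b = 5% v 15% (24.0% v 23.5%) | 0.5 points | 2.5–3.0 |

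**4. Pooled cohort.** Training cases precede randomization at each site (section 4.0). With 600 enrolled (400 AFRS), no true difference, and all 60 training cases at 24 months: (60 × 20% + 400 × 15.2%)/460 − 15.2% = 0.6 points, against AFRS.

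**5. Final analysis.** If 15% are lost evenly over 24 months, crude = 0.85 × 20% + 0.15 × 10.4% = 18.6% under a constant hazard, so a smaller shortfall remains without an early look.

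**The case against.** **A reader might infer that arm differences are understated in general.** The documents do not support that. Randomization is concurrent, 2:1 and blocked within site, so the randomized arms have about the same follow-up. The effect on the difference then depends on event timing, and many of the listed events are surgical. The table in step 3 shows all three outcomes.

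**A reader might infer that only about half of patients have 24 months at any early win.** That holds only for the look at 300 with a final size of 600 or 750. The other early looks give 60–75%, all under assumed even accrual.

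**The AE data cut is inferred.** The win analyses concern the primary endpoint. Section 4.0 follows all treated patients through 24 months, and no visible text freezes the AE tables at a win look. This stands as a condition on the finding. But no visible text names the AE cut-off or commits to a safety update either.

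**Important late events are partly covered.** Serious device-related AEs and index-level reoperations are components of the primary endpoint, whose missing outcomes are predicted. The surgical composite is also analyzed with predictions. AEs are tabulated by period and support no labeling claim. This reduces the impact, but other AEs are not covered, and the by-period tables are not the stated basis of the comparison.

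**Section 8.8 is redacted.** It could contain an adjustment. Against that, section 8.7 attaches predictions to the surgical composite and omits them for AEs.

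**The training-case artefact is small.** It runs against the device, needs all 60 optional cases with full follow-up, and leaves the randomized comparison untouched.

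**Conclusion.** The point holds for the rates. If AE tables are cut at an early win, the stated method understates 24-month incidence in both arms. For a true 20%, the shortfall is about 4.3–5.3 points under a constant hazard (20 − 15.7 to 20 − 14.7) at the look at 300 with N = 600 or 750. It is 6.7–8.3 points if events fall in the second year, and about 2.1 points with N = 450 over 48 months.

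For differences between randomized arms, the supported conclusion is distortion that depends on timing: late differences are attenuated, perioperative ones are about unchanged, and some are exaggerated. The pooled comparison carries an artefact of up to about 0.6 points against AFRS.

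These sizes rest on even accrual over 48–60 months and illustrative AE rates and timing. That the visible plan makes no follow-up adjustment for AEs does not depend on them.

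**What to change.** In section 8.7, base the AE arm comparison on the 24-month cumulative incidence of first event, with death as a competing event, numbers at risk by assessment period, and a 95% credible interval for the difference. Do this for all, serious, device-related and surgery-related AEs, and for the pooled AFRS cohort. Keep crude counts as listings. State the analysis set and data cut-off for the AE tables, and commit to updating them when all treated patients reach 24 months.

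The cost is a few more tables and reported rates somewhat above the crude percentages. No new data are needed: section 1.5 already places events in assessment periods, so a life table on those periods would suffice. Section 8.7 also names a survival method for return to work, although its specification is not visible. Censoring by entry date at an early look is plausibly unrelated to AE risk. Censoring through loss to follow-up may not be, so that assumption should be stated.

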5.6.9 Adverse Events

Adverse events (AEs), including Serious Adverse Events (SAEs), will be captured intraoperatively and during all study follow-up visits. Adverse event definitions and reporting requirements are detailed in Section 6.0: Adverse Event Reporting. All reported AEs will be followed until resolution or completion of the study or postmarket study, as required by FDA.

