6.1.4 Severity

The severity of an adverse event will be assessed according to the World Health Organization (WHO) Recommendations for Grading of Acute and Subacute Toxic Effects. The following definitions are used:

- **Mild (Grade 1):** The adverse event is noticeable to the patient but does not interfere with routine activity. The adverse event does not require implant removal.
- **Moderate (Grade 2):** The adverse event interferes with routine activity but responds to symptomatic therapy or rest. The adverse event does not require implant removal.
- **Severe (Grade 3):** The adverse event significantly limits the patient's ability to perform routine activities despite symptomatic therapy. In addition, the adverse event may require removal of the implant.
- **Life-threatening (Grade 4):** The adverse event may require removal of the implant. The patient is at immediate risk of death.

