6.1.6 Outcome

The outcome of each adverse event will be identified as one of the following categories:

- **Resolved:** The adverse event has been resolved and is no longer continuing
- **Temporary Disability:** Disability that is short term and is not considered a permanent disability
- **Permanent Disability:** Disability that has been determined to be permanent and not temporary
- **Death:** Death of the patient due to the adverse event

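### Adverse-event severity is graded in four levels but analysed in three, and the outcome list has no code for an event that continues without disability

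*Combined protocol and SAP*

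**What the plan says.** **Severity at collection.** Section 6.1.4 opens: "The severity of an adverse event will be assessed according to the World Health Organization (WHO" and so on, and then defines Mild (Grade 1), "Moderate (Grade 2"), "Severe (Grade 3") and Life-threatening (Grade 4). The last has its own definition: "The adverse event may require removal of the implant. The patient is at immediate risk of death".

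**Severity at analysis.** Section 8.7 (Adverse Events) lists the cross-tabulations by treatment group, among them "Severity (Mild, Moderate, Severe"). It then assigns the method: "The statistical method for trichotomous outcomes (e.g., Severity) will be the Bayesian version of a comparison of polytomous outcomes". Classification of severity is given to the Clinical Events Committee (CEC).

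**Outcome.** Section 6.1.6 states: "The outcome of each adverse event will be identified as one of the following categories". The categories are Resolved, Temporary Disability, Permanent Disability and Death. Section 6.1 includes outcome among the items by which adverse events will be tabulated. Section 5.6.9 sets the follow-up rule: "All reported AEs will be followed until resolution or completion of the study or postmarket study, as required by FDA".

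**The concern.** Section 1.3 names severity as one of the measures on which the safety of the device will be judged against fusion, and the Protocol Summary repeats it as a secondary endpoint. If the protocol collects a grade for which the analysis has no level, someone must decide what to do with those events. With no stated rule, that decision could be taken after the data are in. Grade 4 is not a remote category: Section 6.1.1 lists stroke, pulmonary embolism and myocardial infarction among the potential events.

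The outcome list raises a similar problem. An open, non-disabling event fits none of the four codes. The protocol itself generates candidates. Section 5.6.3 makes a fall from baseline in any single neurological measure an adverse event, so a reflex that stays reduced without disabling the patient qualifies. Non-union and adjacent-level degeneration, both listed in Section 6.1.1, can also persist without disability, and they bear on the comparison with fusion. At stake is whether the outcome tabulation can show how many events were still open in each arm.

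**Working it through.** No figure in the plan is at issue, so the check sets the category lists side by side.

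**Step 1: severity.**

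| Level in Section 6.1.4 | Level in Section 8.7 |
|---|---|
| Mild (Grade 1) | Mild |
| Moderate (Grade 2) | Moderate |
| Severe (Grade 3) | Severe |
| Life-threatening (Grade 4) | none |

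Levels collected 4, levels analysed 3; 4 − 3 = 1 level without a cell. Section 8.7 is consistent with itself: the list has three entries and the method sentence uses a word that means three. A slip in one list is therefore an unlikely explanation.

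**Step 2: what happens to Grade 4.** Two courses are open: leave the events out of the severity table, or pool them with Severe. Section 8.7 says that all adverse events will be tabulated, so leaving them out would breach its own opening sentence. Pooling is the reading that fits the text. The top row of the table and of the between-arm comparison would then combine Grades 3 and 4.

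**Step 3: does another output show them?** In part. Section 6.2 makes every life-threatening event serious, and Section 6.1 says that serious events are presented separately, so each Grade 4 event would be in that listing. The seriousness cross-tabulation does not isolate them, because inpatient hospitalization alone also makes an event serious under Section 6.2.

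**Step 4: outcome.** Take each possible status of an event at last contact.

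| Status at last contact | Code in Section 6.1.6 |
|---|---|
| Over | Resolved |
| Continuing, with disability | Temporary or Permanent Disability |
| Fatal | Death |
| Continuing, without disability, not fatal | none |

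Resolved cannot serve for the fourth row, because its definition requires that the event has ceased. Section 5.6.9 allows follow-up of an event to end at study completion instead of at resolution, so the plan expects the fourth row to occur. Events open when a patient withdraws or is lost (Section 5.7) can fall into it too.

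**Step 5: reach.** The primary endpoint (Section 3.5.1) uses seriousness and device-relatedness, not the severity grade or the outcome code. Section 8.7 reserves labeling claims for the first five secondary objectives, and adverse events are not among them. Neither list enters the sample size algorithm in Section 8.3. The documents give no event counts, so the number affected cannot be calculated.

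**The case against.** The strongest reply is that little turns on either list. All adverse events are to be tabulated, the CEC classifies severity for analysis, and serious events and deaths are presented separately. Section 6.1 also promises a tabulation by severity, and the protocol's severity scale is the four-grade one. On that view the only gap is an unstated merging rule. Most of this stands and limits the size of the point. It does not remove the contradiction: Section 8.7 fixes three levels twice, and a tabulation promised in Section 6.1 does not amend the comparison defined in Section 8.7.

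A second reply concerns what cannot be seen. Section 8.8, where the polytomous comparison would be described, is not in the public copy, and form SA10 is not shown. A merging rule or a continuing box may exist there. That is fair, and neither can be called absent from the plan. Even so, the wording of Sections 8.7 and 6.1.6 would have to be brought into line with them.

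A third reply is that outcome is not among the cross-tabulations in Section 8.7, and that a neurological decline is captured elsewhere, as a 24-month secondary test and a CEC-adjudicated component of the primary endpoint. Both statements are correct. The gap then concerns the Section 6.1 tabulation only, and it covers non-neurological events as well.

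A reader might infer more than this in three ways, and the documents do not support any of them:

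- *Life-threatening events would be dropped.* The promise to tabulate all events points to pooling, and the serious-event listing keeps them visible.
- *Open events would necessarily be miscoded as Resolved or as disability.* The outcome could equally be left blank, and the form is not available to settle it.
- *The method must become an ordered one.* Nothing readable shows that the planned polytomous comparison is unsuitable, and it is not inherently limited to three levels.

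**Conclusion.** The point holds and is minor: the text is wrong as written in two places. Section 8.7 has no level for one of the four severity grades that Section 6.1.4 collects. As written, that grade would most likely be merged into Severe, and the between-arm severity table would not show life-threatening events separately. Section 6.1.6 gives no valid code to an event that continues without disability at last contact, a situation that Section 5.6.9 foresees.

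The consequence is limited to safety reporting. The primary endpoint, the sample size and the labeling claims do not change. The conclusion rests on the readable lists and assumes that no rule or code in the unseen Section 8.8 or form SA10 already closes the gap. If one does, what remains is to align the wording.

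**What to change.** - **Section 8.7.** List four severity levels (Mild, Moderate, Severe, Life-threatening), replace trichotomous with polytomous, and keep the planned polytomous comparison. If Grade 4 is to be pooled with Severe for the model, state this in advance and still show Grade 4 as its own row by arm.
- **Section 6.1.6, and form SA10 if it is not already there.** Add an outcome category for events that are ongoing or not resolved at last contact, and tabulate it by arm.

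The cost is a few words in the SAP, one more row in the severity table, one more outcome category and, if needed, one more option on the form. Treatment, visits and sample size are not touched.
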